7.1.7 Side Effects

Reactions to NAROPIN (ropivacaine hydrochloride) are characteristic of those associated with other long-acting local anesthetics of the amide type.

In clinical trials, the great majority of adverse events reported with ropivacaine were related to the expected effects of the block and to the clinical situation, rather than reactions to the drug.

When all clinical studies were pooled (total n=3056), hypotension and nausea were registered in 41.2% (n=1259) and 28.4% (n=867) of the patients, respectively. Similar incidences were reported for bupivacaine in the double-blind comparisons.

Adverse reactions to local anesthetics are very rare in the absence of overdose or inadvertent intravascular injection. The effects of systemic overdose and unintentional intravascular injections can be serious, but should be distinguished from the physiological effects of the nerve block itself (e.g. a decrease in blood pressure, bradycardia, urinary retention after epidural and intrathecal block), and events caused directly by needle puncture (e.g. spinal haematoma, postdural puncture headache), or indirectly by introduction of micro-organisms (e.g. meningitis and epidural abscess).

Acute systemic toxicity from local anaesthetics is generally dose-related and due to high plasma levels which may result from overdosage (see OVERDOSAGE), rapid absorption from the injection site, diminished tolerance, or from inadvertent intravascular injection. Most commonly, the acute adverse experiences originate from the central nervous and cardiovascular systems.

7.1.8 Overdosage

Systemic toxic reactions primarily involve the central nervous system and cardiovascular system. Such reactions are caused by high plasma levels encountered during therapeutic use, overdose, or to unintended intravascular or subarachnoid injection (see ADVERSE REACTIONS and WARNINGS AND PRECAUTIONS). CNS reactions are similar for all amide local anesthetics, while cardiac reactions are more dependent on the drug, both quantitatively and qualitatively.

Symptoms

Accidental intravascular injections may cause immediate (within seconds to a few minutes) toxic effects. In the event of overdose, peak plasma concentrations may not be reached for 1 to 2 hours, depending on the site of injection, with signs of toxicity thus being delayed.

Central nervous system toxicity is a graded response with symptoms and signs of escalating severity. First symptoms are usually light-headedness, circumoral paraesthesia, numbness of the

tongue, hyperacusis, tinnitus and visual disturbances. Dysarthria, muscular rigidity and muscular twitching are more serious and may precede the onset of generalized convulsions. These signs must not be mistaken for a neurotic behavior. Unconsciousness and grand mal convulsions may follow which may last from a few seconds to several minutes. Hypoxia and hypercarbia occur rapidly following convulsions due to the increased muscular activity, together with the interference with normal respiration and loss of the airway. In severe cases apnea may occur. Acidosis, hyperkalemia, hypocalcemia and hypoxia increase and extend the toxic effects of local anesthetics.

Recovery is due to redistribution and metabolism of the local anesthetic drug. Recovery may be rapid unless large amounts of the drug have been administered.

Cardiovascular system toxicity indicates a more severe situation and is generally preceded by signs of toxicity in the central nervous system, unless the patient is receiving a general anesthetic or is heavily sedated with drugs such as a benzodiazepine or barbiturate. Hypotension, bradycardia, arrhythmia and cardiac arrest may occur as a result of high systemic concentrations of local anesthetic. In volunteers, the intravenous infusion of ropivacaine resulted in signs of depression of conductivity and contractility.

In children early signs of local anesthetic toxicity may be difficult to detect in cases where the block is given during general anesthesia. It should be noted that NAROPIN (ropivacaine hydrochloride) is not approved for use in pediatric patients.

Treatment

The first consideration is prevention, best accomplished by incremental injection of NAROPIN, careful and constant monitoring of cardiovascular and respiratory vital signs and the patient's state of consciousness after each local anesthetic injection and during continuous infusion. At the first sign of change, oxygen should be administered. If signs of acute systemic toxicity appear, injection of the local anesthetic should be immediately stopped.

The first step in the management of systemic toxic reactions, as well as hypoventilation or apnea due to unintentional subarachnoid injection of drug solution, consists of immediate attention to the establishment and maintenance of a patent airway and assisted or controlled ventilation with oxygen and a delivery system capable of permitting immediate positive airway pressure by mask and bag or tracheal intubation. This may prevent convulsions if they have not already occurred.

If necessary, use drugs to control the convulsions. An anticonvulsant should be given i.v. if the convulsions do not stop spontaneously in 15-20 seconds. Thiopental 1–3 mg/kg i.v. will abort the convulsions rapidly. Alternatively, diazepam 0.1 mg/kg i.v. may be used, although its action will be slow. Both these drugs, however, depress the central nervous system, respiratory and cardiac functions, add to postictal depression, and may result in apnea.

Prolonged convulsions may jeopardize the patient's ventilation and oxygenation. If so, injection of a muscle relaxant such as succinylcholine (1 mg/kg) will stop the muscle convulsions rapidly,

so that ventilation and oxygenation can be controlled. Endo-tracheal intubation must be considered in such situations.

If cardiovascular depression is evident (hypotension, bradycardia) administration of intravenous fluids or a vasopressor such as ephedrine or epinephrine may be required.

Should circulatory arrest occur, immediate cardiopulmonary resuscitation should be instituted. Optimal oxygenation and ventilation and circulatory support as well as treatment of acidosis are of vital importance.

Should cardiac arrest occur, prolonged resuscitative efforts may be required to improve the likelihood of a successful outcome.

Clinical data from patients experiencing local anesthetic-induced convulsions demonstrated rapid development of hypoxia, hypercarbia, and acidosis within a minute of the onset of convulsions. These observations suggest that oxygen consumption and carbon dioxide production are greatly increased during local anesthetic convulsions and emphasize the importance of immediate and effective ventilation with oxygen, which may avoid cardiac arrest.

In human volunteers given intravenous NAROPIN, the mean maximum tolerated total and free arterial plasma concentrations were 4.3 and 0.6 $\mu\text{g/mL}$ respectively, at which time moderate CNS symptoms (muscle twitching) were noted.

7.2 Placebo

Patients randomized to the placebo group will be administered 0.9% sodium chloride solution at a dose of 0.8 mL/kg, using the technique described in the treatment administration section (section 5.7).

7.3 Opioid use

Other opioid use such as IV PCA (morphine) and PO opioids (oxycodone) will be standardized by conversion into morphine equivalents based on a 24-hour regimen using Table 4.

Table 4. Standardization table for Opioid use by participants based on the “Equianalgesic Dosing of Opioids for Pain Management*.”

Morphine (mg/day)		Oxycodone (mg/day)	
Oral	IV	Oral	IV
45-134	8-22	22.5-67	12-33
135-224	23-37	67.5-112	33.1-56
225-314	38-52	112.5-157	56.1-78
315-404	53-67	157.5-202	78.1-101
405-494	68-82	202.5-247	101.1-123
495-584	83-97	247.5-292	123.1-147
585-674	98-112	292.5-337	147.1-168
675-764	113-127	337.5-382	168.1-191
765-854	128-142	382.5-427	191.1-213
855-944	143-157	427.5-472	213.1-236
945-1034	158-172	472.5-517	236.1-258
1035-1124	173-187	517.5-562	258.1-281

*http://pharmacy.uams.edu/formulary/narc_conv_chart.htm

8. Administrative Procedures

8.1 Protocol Amendments

Any changes to the protocol will be made in the form of an amendment and must be approved by the IRB prior to implementation.

8.2 Informed Consent

The investigator or other qualified study team member will explain to each subject the nature of the study, its purpose, the procedures involved, the expected duration of study participation, the potential risks and benefits involved and any discomfort it may entail. Each subject will be informed that participation in the study is voluntary and that he/she may withdraw from the study at any time and that withdrawal of consent will not affect his/her subsequent medical treatment or relationship with the treating physician or institution. The informed consent will be given by means of a standard written statement, written in non-technical language, which will be IRB approved. No subject will enter the study before his/her informed consent has been obtained.

In accordance with the Health Information Portability and Accountability Act (HIPAA), the written informed consent document will include a subject authorization to release medical information to the study sponsor and supporting agencies and/or allow these bodies, a regulatory authority, or Institutional Review Board access to subjects' medical information that includes all hospital records relevant to the study, including subjects' medical history.

8.3 Ethics and Good Clinical Practice

This study will be carried out in compliance with the protocol and Good Clinical Practice, as described in the following:

1. ICH Harmonized Tripartite Guidelines for Good Clinical Practice 1996.
2. US 21 Code of Federal Regulations dealing with clinical studies (including parts 50 and 56 concerning informed consent and IRB regulations).
3. Declaration of Helsinki, concerning medical research in humans (Recommendations Guiding Physicians in Biomedical Research Involving Human Subjects, Helsinki 1964, amended Tokyo 1975, Venice 1983, Hong Kong 1989, Somerset West 1996).

The investigator agrees to adhere to the instructions and procedures described herein and, thereby, to adhere to the principles of Good Clinical Practice to which it conforms.

9. Adverse Events

9.1 General

This study is collecting data regarding post-operative pain after a planned surgical procedure. The placement of the paravertebral block and ropivacaine is not expected to cause increased side effects or problems than those already anticipated with surgery. Subjects randomized to the placebo group will be at increased risk of harm related to the subcutaneous paravertebral saline injections without the chance of benefit. Any events that occur that are deemed "unexpected" to

the surgical procedure(s) performed, but related to the study procedures will be reported per current institutional requirements.

9.2 Definitions

9.2.1 Adverse Event (AE)

Any undesirable sign, symptom or medical condition occurring after starting study drug (even if the event is not considered to be related to the study) is considered an adverse event. An undesirable medical condition can be symptoms (e.g., nausea, chest pain), signs (e.g., tachycardia, enlarged liver), or the abnormal results of an investigation (e.g., laboratory findings, electrocardiogram).

Medical conditions/diseases present before starting study treatment are only considered adverse events if they worsen after starting study treatment (any procedures specified in the protocol). Adverse events occurring before starting study treatment but after signing the informed consent form will be recorded. Abnormal laboratory values or test results constitute adverse events only if they induce clinical signs or symptoms or require therapy.

9.2.2 Serious Adverse Event or Reaction

A serious adverse event is an undesirable sign, symptom or medical condition which:

- Is fatal or life-threatening;
- Required or prolonged hospitalization;
- Results in persistent or significant disability/incapacity;
- Constitutes a congenital anomaly or a birth defect;
- Is medically significant, may jeopardize the subject and may require medical or surgical intervention to prevent one of the outcomes listed above.

Events **not** considered to be serious adverse events are hospitalizations for:

- Routine treatment or monitoring of the studied indication not associated with any deterioration in condition, or for elective procedures (i.e., venous access placement, etc.).
- Treatment, which was elective or pre-planned, for a pre-existing condition that did not worsen.
- Treatment on an emergency, outpatient basis for an event **not** fulfilling any of the definitions of serious given above and **not** resulting in hospital admission.

The definition of serious adverse event (experience) also includes *important medical event*. Medical and scientific judgment should be exercised in deciding whether expedited reporting is appropriate in other situations, such as important medical events that may not be immediately life-threatening or result in death or hospitalization but may jeopardize the patient or may require intervention to prevent one of the other outcomes listed in the definition above. These should also usually be considered serious. Examples of such events are intensive treatment in an emergency room or at home for allergic bronchospasm; blood dyscrasias or convulsions that do not result in hospitalization; or development of drug dependency or drug abuse.

9.2.3 Expectedness

- 9.2.3.1 Unexpected adverse event: An adverse event, which varies in nature, intensity or frequency from information on the investigational drug/agent provided in the Investigator's Brochure, package insert or safety reports. Any adverse event that is not included in the informed consent is considered "unexpected".
- 9.2.3.2 Expected (known) adverse event: An adverse event, which has been reported in the Investigator's Brochure. An adverse event is considered "expected", only if it is included in the informed consent document as a risk.

9.3 Relationship

The relationship of all adverse events and serious adverse events to study medication will be assessed by an investigator and assigned as follows:

- 9.3.1 Definitely: An adverse event which has a timely relationship to the administration of the investigational drug/agent, follows a known pattern of response, and for which no alternative cause is present.
- 9.3.2 Probably: An adverse event which has a timely relationship to the administration of the investigational drug/agent, follows a known pattern of response, but for which a potential alternative cause may be present.
- 9.3.3 Possibly: An adverse event which has a timely relationship to the administration of the investigational drug/agent, follows no known pattern of response, but a potential alternative cause does not exist.
- 9.3.4 Unlikely: An adverse event which does not have a timely relationship to the administration of the investigational drug/agent, follows no known pattern of response, does not reappear or worsen after re-administration of the investigational drug/agent (if applicable), and for which there is evidence that it is related to a cause other than the investigational drug/agent.
- 9.3.5 Unrelated: An adverse event for which there is evidence that it is definitely related to a cause other than the investigational drug/agent. In general, there is no timely relationship to the administration of the investigational drug/agent, or if there is a timely relationship, the event does not follow a known pattern of response, and there is an alternative cause.

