5.8 Justification For Placebo

In clinical trials of surgical interventions, sham procedure is an important scientific control. The sham paravertebral subcutaneous saline injections will contribute to isolate the specific effects of the treatment drug (ropivacaine hcl) as opposed to the patient's perception of having had a regular paravertebral block. Thus, sham paravertebral subcutaneous saline injections serve an analogous purpose to placebo drugs, neutralizing biases such as the placebo effect. Additionally, the subcutaneous paravertebral injections of placebo (normal saline) do not carry increased risks besides the potential risks of the injection process itself. The potential risks associated with the injection process itself include the risk of inadvertent vascular puncture (6.8%), pleural puncture (0.8%) and pneumothorax (0.5%),²⁶ all of which are classified as unlikely events (occurring in 1-10 of every 100 patients). Hence, the administration of placebo will strengthen the study design and any conclusion reached without significantly increasing the risk of complications.

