9.4.3 Food and Drug Administration (FDA)

In this trial using a medication for an FDA-approved indication, unexpected adverse events believed to be definitely, probably, or possibly related to the medication (s) will be reported to the Food and Drug Administration via Med Watch (using the online form available at <https://www.accessdata.fda.gov/scripts/medwatch/>; by telephone [name]; or by fax [name] using form available at <http://www.fda.gov/medwatch/report/hcp.htm>). This reporting mechanism will be used to report events that may be related to the use of the ropivacaine.

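### Section 9.3 lets Probably coexist with another possible cause but forbids one for Possibly, so a new type of drug reaction can miss the FDA route; it also has no rating for the injection procedure

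*Combined protocol and SAP*

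**What the plan says.** Section 9.3 opens: "The relationship of all adverse events and serious adverse events to study medication will be assessed by an investigator". Five grades follow, built from three features: timing, known pattern of response, and alternative cause.

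- **Definitely**: timely, known pattern, no alternative cause.
- **Probably**: timely, and the event "follows a known pattern of response, but for which a potential alternative cause may be present".
- **Possibly**: timely, and the event "follows no known pattern of response, but a potential alternative cause does not exist".
- **Unlikely**: not timely, no known pattern, with evidence of another cause.
- **Unrelated**: the lead sentence requires "evidence that it is definitely related to a cause other than the investigational drug/agent". A further sentence, introduced as a generality, describes events with no timely relationship, "or if there is a timely relationship, the event does not follow a known pattern of response, and there is an alternative cause".

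Three other sections depend on relatedness or expectedness. Section 9.4.3 sets the FDA gate: "unexpected adverse events believed to be definitely, probably, or possibly related to the medication (s) will be reported". Its closing sentence describes the route more loosely, as one for events with a possible link to ropivacaine. Section 9.2.3 calls an event unexpected if it is one "which varies in nature, intensity or frequency from information on the investigational drug/agent", or if the consent form does not list it. Section 9.1 sends events that are unexpected for the surgery but related to the study procedures to institutional reporting.

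**The concern.** The scale should loosen as it descends from Definitely to Possibly. On alternative causes it tightens instead: Probably accepts a rival explanation and Possibly does not. Possibly is the only reportable grade open to an event with no known pattern, because Definitely and Probably both require one. A reaction of a kind not seen before with the drug must therefore be free of any rival explanation to be reported. In this trial that condition can hardly be met.

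The second gap is that 9.1 asks whether an event is related to a study procedure, and 9.3 offers no scale for that question. Every grade is worded against the drug, yet both arms receive needle injections that are part of the study, and 9.1 itself says the placebo arm carries their risk without a chance of benefit.

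At stake are the external reporting of a new drug signal and a consistent record of which events the block or sham injection caused.

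**Working it through.** The plan states no figure to reproduce here. The check applies the 9.3 definitions to every timely combination of pattern and alternative cause, then applies the 9.4.3 gate.

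| Known pattern | Alternative cause | Grade under 9.3 | Passes 9.4.3 if unexpected |
|---|---|---|---|
| yes | none | Definitely | yes |
| yes | potential | Probably | yes |
| yes | definite | Probably and Unrelated both fit | only if Probably is chosen |
| no | none | Possibly | yes |
| no | potential | Unrelated by the general clause, or no grade if read strictly | no |
| no | definite | Unrelated | no |

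The fifth row is the defect. Unlikely cannot take the event, because that grade needs the timing to be wrong.

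**How often a potential alternative cause is present.** Under section 5.7 every patient receives midazolam, fentanyl and local lidocaine, then the study injections, then general anesthesia at once, then surgery. A potential rival cause is present in nearly every patient, so a timely event without a known pattern will usually fall in the fifth row or below it.

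**Which unexpected events are exposed.** Section 9.2.3 gives several routes to unexpectedness. An event that differs only in intensity or frequency, or that is merely absent from the consent form, can still follow a known pattern. It is then Probably (second row) and passes the gate. Only events unexpected in nature are caught.

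**Procedure attribution.** Section 7.1.7 separates events caused directly by needle puncture from drug effects. A needle injury therefore has a definite non-drug cause and is Unrelated under the lead sentence of 9.3.5. As a statement about ropivacaine that is accurate. It leaves open the question that 9.1 asks.

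For scale only, section 5.8 lists vascular puncture (6.8%), pleural puncture (0.8%) and pneumothorax (0.5%) as risks of the injection process. Assume these are rates per patient. Expected count = n × rate:

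- All 70 patients: 70 × 0.068 = 4.76; 70 × 0.008 = 0.56; 70 × 0.005 = 0.35.
- Block arm only, 35 patients: 35 × 0.068 = 2.38; 35 × 0.008 = 0.28; 35 × 0.005 = 0.175.

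The sham is subcutaneous, so its true rates may be lower, and the range from 35 to 70 patients allows for that. These counts show how many events might need a procedure rating. They do not count lost FDA reports.

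**The case against.** The strongest reply is that little depends on the 9.3 grade. Section 9.4.1 captures all adverse events on CRFs and sends every SAE to the principal investigator whatever its cause. Section 9.4.2 sends all events to the IRB. Section 10.2 compares the proportions of patients with specific event types by arm, using chi-square or Fisher's exact tests, with no relatedness filter. All of this stands. A reader might infer that the block-versus-sham safety comparison would understate harm. It would not: a pneumothorax counts in its arm whatever its grade, and no causality-graded table is planned.

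A reader might also infer that needle injuries drop out of FDA reporting because of the scale. The documents do not support that. Section 9.4.3 covers the medication only, so such injuries lie outside it by scope. Those listed in the consent form would also be expected; the consent pages are not available to check.

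A third reply is that 9.3.5 does not force an event into Unrelated, since its lead sentence demands definite evidence of another cause and the later sentence is only a generality. That is fair, and it is why the fifth row carries two readings. It does not rescue the rule: an event that fits no grade is not Definitely, Probably or Possibly related either.

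Finally, the looser closing sentence of 9.4.3 gives an investigator a basis to report anyway. It does, but it then conflicts with the grade-based gate in the same section, and a reporting rule should not depend on which sentence is followed.

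**Conclusion.** The concern holds in a limited form. Section 9.3 is inverted on alternative causes, and a timely, new-type event with a potential rival explanation misses the 9.4.3 gate on either reading of 9.3.5. That runs against the intent in the closing sentence of 9.4.3. Section 9.3 also lacks the procedure rating that 9.1 needs.

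The effect has two parts: MedWatch reporting of new-type drug events, and attribution to the block or sham under 9.1. The first rests on a potential alternative cause being almost always present, which the schedule in 5.7 supports. Its frequency cannot be estimated, because the documents give no rate for new-type reactions. It would go too far to say that all unexpected events are lost, since those with a known pattern can still be graded Probably. Event capture, IRB reporting and the arm comparison are sound. The fault is worth correcting because a stated safety rule gives the wrong classification and the remedy is cheap.

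**What to change.** 1. Reword 9.3.3 so that Possibly covers a timely event, with or without a known pattern, where an alternative cause may be present but does not clearly explain the event.
2. Limit Unrelated in 9.3.5 to events clearly explained by another cause, and delete its clause on timely events without a known pattern.
3. State the order of use, because the reworded Possibly overlaps with Probably: first ask whether another cause clearly explains the event; if not, assign the highest grade whose conditions are met. This also settles the double fit in the third row of the table.
4. Add a separate causality rating on the CRF for the study injection procedure (block or sham), and refer to it in 9.1.

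With these changes the fifth row becomes Possibly and passes the gate, so the two sentences of 9.4.3 agree. The cost is a wording amendment and one CRF field, with a few more events graded possibly related and reported. Treatment, endpoints and sample size do not change.
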